Pain is the most commonly reported complication associated with the use of tissue expanders, and yet suboptimal pain control with the use of oral narcotics remains the current standard of care. Over the years, numerous methods to decrease pain associated with the process of tissue expansion have been tested and yielded unsatisfactory results.^{2-5, 10, 49} For example, Sinow et al. experimented with intraluminal injections of lidocaine in tissue expanders, but were unable to demonstrate any reduction in pain when lidocaine was compared with placebo.² Moreover, in recent years, innovation in prosthetic breast reconstruction techniques has seen a rapid rise in popularity of acellular dermal matrix (ADM).⁵⁰⁻⁵³ Many plastic surgeons have incorporated ADM in their surgical practice for one-stage and two-stage prosthetic breast reconstruction.⁵⁴⁻⁵⁶ ADM is frequently used as a sling to cover the lower lateral pole of tissue expanders and implants in breast reconstruction.⁵⁷ Potential benefits may include: 1) improved control of the submuscular pocket and infra-mammary fold;^{57, 58} 2) higher initial filling volumes of tissue expanders at the time of placement; 3) reduced overall number of expansions; and 4) decreased pain morbidity associated with the musculofascial dissection (rectus abdominus and serratus anterior). At the present time, possible benefits of ADM on postoperative pain alleviation have not been demonstrated in prospective clinical trials. The research proposed in this application is innovative, in our opinion, because it represents a new and substantive departure from the status quo in pain management following tissue expander breast reconstruction. An additional strength of this investigation is that it will include a newly developed patient-reported outcome (PRO) measure to study physical well-being. The BREAST-Q® was rigorously developed and validated with adherence to guidelines set by the Medical Outcomes Trust⁵⁹ and the FDA.⁶⁰

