5.6 Prior and Concomitant Therapy

As part of the standard of care at Mayo Clinic, patients are offered optional regional anesthesia in the form of a thoracic paravertebral block (PVB) on the morning of surgery, in addition to the routine procedures. The PVB technique^{74, 75} used includes multilevel injections of 1% to 0.5% ropivacaine with 1:400,000 epinephrine into the ipsilateral paravertebral space at six levels from T1 through T6. This technique can improve postoperative pain control for 4 to 8 hours after performance of the PVB. The data on PVB will be collected as it can act as a potential confounding variable.

Depending on individual surgeon practice and preference, some patients may receive other forms of short-term intraoperative local analgesia such as Exparel, an injectable suspension of bupivacaine liposome which can provide pain relief for up to 72 hours. Data on Exparel will also be collected as it can act as a potential confounding variable.

Additional oral analgesic intake by study participants will not be monitored as this data collection is often incomplete and of poor quality, making it difficult or impossible to draw any reliable conclusions. Thus, oral analgesic intake will not be restricted during the course of this study.

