5.9.4 Return or Destruction of Study Drug

At the completion of the study, there will be a final reconciliation of drug shipped, drug consumed, and drug remaining. This reconciliation will be logged on the drug reconciliation form, signed and dated. Any discrepancies noted will be documented and investigated, prior to return or destruction of unused study drug. Drug destroyed on site will be documented in the study files.

6 Study Procedures

TABLE OF VISITS:

	Research activity	Subject activity
Preoperative evaluation/Surgical listing appointment	Study Coordinator (SC) reviews the study with eligible patients and obtains informed consent	Complete the BREAST-Q and Numeric Pain Intensity Scale
Surgery	Randomization by site specific research pharmacy and intra-operative injection of study drug by plastic surgeon	•
First post-operative visit: • Week 1- 2	SC facilitates completion of questionnaire and assesses for adverse events	Complete the BREAST-Q and Numeric Pain Intensity Scale
Subsequent Plastic Surgery Appointments/Expansion Visits • Beginning at week 2-3 and intervals thereafter as determined by the plastic surgeon	SC facilitates completion of questionnaire and assesses for adverse events	Complete the BREAST-Q and Numeric Pain Intensity Scale
• End of Study • The last plastic surgery appointment prior to removal of the TE, or the date of TE removal (whichever occurs last within the 4 month postoperative period)		

Tissue expander placement: The surgical procedure for submuscular placement of the tissue expander will be performed in the usual manner by each participating plastic surgeon.

BTX-A Injection Protocol: see Section 5.4

Outcome Assessment: The outcome measures selected to test our working hypothesis and answer our specific aim #1 are a numeric pain intensity scale (NPIS)⁷¹, and the Physical Well-Being scale of the BREAST-Q®: Reconstruction Module. These two measures will be administered to study participants at the pre-operative visit, the first postoperative visit (1-2 weeks), and subsequent Plastic Surgery appointments/expansion visits until the end of the study is reached.

7 Statistical Plan

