There are two primary outcomes: pain intensity measured by the NPIS, and physical well-being using the BREAST-Q®. The primary analysis will be performed during the post-operative period and during the expansion phase. Outcome variables will be summarized with frequency counts and percentages or means, standard deviations, medians, and ranges, as appropriate. The mean, median, standard deviation, and range of each variable and its change from baseline, measured on a continuous scale, will be presented by treatment and visit. Frequency tables will be provided for categorical variables by treatment and visit. Any differences among the study groups will be evaluated using two-sample t, Wilcoxon rank sum, Pearson's chi-square, or Fisher's exact tests.

Secondary Hypotheses:

- 1) There will be no difference in the initial percent volume expansion between groups (defined as initial intraoperative fill volume divided by manufacturer recommended total tissue expander volume);
- 2) The rate of tissue expansion will be higher in the BTX-A groups compared to the placebo group, with or without the use of ADM;
- 3) There will be no difference in the rate of reconstructive failure (tissue expander removal for reasons such as infection or uncontrolled pain).

The volume of tissue expansion anticipated and the rate of tissue expansion between the BTX-A groups and the placebo and control groups will be calculated both as an absolute value as well as a percentage. It is hypothesized that the use of BTX-A may increase the rate of tissue expansion, which may lead to fewer postoperative tissue expansion visits. This will allow measurement of effect size between the intervention and the placebo groups. Two-sample t and Wilcoxon rank sum tests will be used for the secondary analyses.

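### Expansion rate, the one secondary endpoint predicted to differ, is compared without adjustment for surgeon or acellular dermal matrix, which may give up precision of unknown size

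*Combined protocol and SAP*

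**What the plan says.** Section 7.2 (Secondary Hypotheses) sets three expectations:

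- Initial fill: "There will be no difference in the initial percent volume expansion between groups".
- Expansion rate: "The rate of tissue expansion will be higher in the BTX-A groups compared to the placebo group, with or without the use of ADM".
- Failure: "There will be no difference in the rate of reconstructive failure".

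Only the second predicts a difference. The method for the secondary endpoints is one sentence: "Two-sample t and Wilcoxon rank sum tests will be used for the secondary analyses". It has no covariate or stratum. The rate is to be calculated in absolute and percentage terms; its time denominator and the handling of bilateral cases are not given.

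On what else may move the rate:

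- The Table of Visits in section 6 schedules expansion visits thus: "Beginning at week 2-3 and intervals thereafter as determined by the plastic surgeon". Sections 3.1 and 6 make clear that more than one surgeon takes part.
- Section 1.1 lists higher initial fill and "reduced overall number of expansions" among the possible benefits of ADM.
- Section 5.3 allows ADM in either arm and describes randomisation by a random-number program. No stratification by surgeon or ADM is stated.
- Section 5.5 says some women will have expansions at outside institutions.

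The descriptive part of section 7.2 does provide for covariates, but only in sensitivity analyses and only if the baseline tables suggest a need. Its open-ended list names ADM use and initial percent volume expansion. It does not name surgeon.

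**The concern.** Any rate has time underneath it, so a schedule that differs between surgeons enters the endpoint directly. ADM may act on it too, through starting volume and number of expansions. In a two-sample test, whatever variation these factors cause stays in the error term. Pre-specified adjustment removes it even when the arms are well balanced. Adjustment that waits for a visible imbalance misses that benefit and leaves the choice until after the data have been seen. At stake is the width of the confidence interval, and so the chance of detecting a BTX-A effect on the one secondary endpoint where the plan expects one.

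**Working it through.** **Inputs from the documents.** 64 women per arm with complete data (128 of 134 enrolled; 1 − 128/134 = 4.5% allowance), significance level 0.05 and 80% power, all from section 7.1. These were set for pain. No mean, SD, target difference or power is given for expansion rate.

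**The plan's own figure.** For pain 4.0 v 3.0 with SD 2.0, the normal approximation is n = 2 × (1.960 + 0.842)² × 2.0² / 1.0² = 62.8, so 63 per group. The exact two-sided t-test gives 63.77, so 64, as stated. The other five entries (17, 26, 100, 37, 143) also reproduce exactly with the t-test.

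**Effect of adjustment.** Let R² be the share of expansion-rate variance explained by surgeon and ADM. Adjustment multiplies the residual SD by √(1 − R²).

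- Difference detectable with 80% power at 64 per arm: 0.499 × √(1 − R²) SD.
- Power for a true difference of 0.4 SD: Φ(0.4 / [√(1 − R²) × √(2/64)] − 1.96). At R² = 0 this is Φ(2.263 − 1.96) = 61.9%. At R² = 0.3 it is Φ(2.705 − 1.96) = 77.2%.

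The formula ignores the cost of estimating the extra coefficients. A simulation that includes this cost was run, with 4,000 runs per cell, six surgeons, ADM in half the women, unstratified 1:1 allocation, and explained variance split 60:40 between surgeon and ADM.

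| R² (assumed) | Detectable difference | Power at 0.4 SD, formula | Simulated t-test | Simulated adjusted model |
|---|---|---|---|---|
| 0 | 0.50 SD | 61.9% | 62.4% | 60.3% |
| 0.1 | 0.47 SD | 66.5% | 61.6% | 64.2% |
| 0.3 | 0.42 SD | 77.2% | 62.0% | 74.7% |
| 0.5 | 0.35 SD | 89.3% | 61.7% | 86.9% |

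In the simulation, adjustment therefore loses about 2 points at R² = 0, and gains about 3 points at 0.1, 13 at 0.3 and 25 at 0.5. The Monte Carlo standard error of one cell is about √(0.62 × 0.38 / 4000) = 0.8 points, so the smallest differences are approximate.

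**Validity of the planned test.** With no true difference, the simulated t-test rejected in 4.7% to 5.1% of runs across the four values of R².

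**Assumptions.** R², the 0.4 SD difference, the number of surgeons, the ADM share and the 60:40 split are all assumed; the documents give none of them.

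**The case against.** The strongest reply is that an unadjusted comparison of randomised arms is valid, the endpoint is secondary and was never powered, and nothing in the documents shows that the gain is material. At R² = 0.1 it is only two or three points. All of this stands, and it limits the point to a cheap improvement.

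Four further objections have some force.

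- Section 7.2 already lists ADM use and initial fill as candidate covariates, and the list is open-ended. So ADM is not ignored. But the provision is conditional, omits surgeon by name and leaves the main test unchanged.
- The hypothesis speaks of both ADM settings, which could be read as an intention to analyse within them. The methods sentence names no such analysis.
- Some expansions take place elsewhere (section 5.5), so the operating surgeon is an imperfect marker of schedule. This reduces the likely gain.
- Section 7.2 suggests BTX-A may lead to fewer expansion visits, so schedule may be part of the route of effect. That is a reason not to adjust for observed visit intervals. It does not apply to the identity of the operating surgeon.

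Stronger readings are tempting but unsupported. A reader might infer that surgeon and ADM largely determine the rate; the documents say only that surgeons set intervals and that ADM may have these benefits, with no variance share. A reader might also infer that a chance imbalance of surgeons would pass for a drug effect; such imbalance is already covered by the test's nominal error rate, as the simulation shows. The remark on surgeon preference in section 5.6 concerns intraoperative analgesia and is not evidence about expansion. Nor does the argument extend to the primary outcomes, for which section 7.2 specifies two-sample tests and no regression model to which surgeon could be added.

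**Conclusion.** The point holds as one of lost precision, not bias. The main comparison of expansion rate leaves out two factors that the protocol itself links to expansion, and the sensitivity provision does not make good the loss. How much is lost cannot be read from the documents. Under the assumptions shown, at 64 per arm and a 0.4 SD difference, adjustment moves simulated power from about 62% to about 64% if surgeon and ADM explain 10% of the variance and to about 75% if they explain 30%. If they explain nothing, it costs about 2 points. This is a minor, inexpensive improvement to a secondary analysis.

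**What to change.** In section 7.2, pre-specify before unblinding, and whatever imbalance is seen, a linear model as the main analysis of expansion rate:

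- One value per woman, with the volume measure, the time denominator and the way bilateral cases are combined all stated. Say how expansions at outside institutions are counted.
- Terms for treatment, operating surgeon (low-volume surgeons pooled by a stated rule) and ADM use.
- Report the adjusted difference with its 95% confidence interval.
- Keep the t and Wilcoxon tests as supportive analyses.

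Before adopting the ADM term, confirm that ADM use is decided without knowledge of allocation. Section 5.3 says the surgeon is masked at injection, which supports this, but the documents do not say when or by whom ADM use is decided.

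The cost is SAP wording and a few degrees of freedom. ADM use is already among the variables to be described, and the operating surgeon should be available from the operative record.

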7.3 Subject Population(s) for Analysis

The subject populations whose data will be subjected to the study primary and secondary analyses will include all randomized populations.

8 Safety and Adverse Events

8.1 Definitions

Adverse Event: An untoward or undesirable experience associated with the use of a medical product (i.e. drug, device, biologic) in a patient or research subject.

Note: An adverse event (also referred to as an adverse experience) can be any unfavorable and unintended sign (e.g., an abnormal laboratory finding), symptom, or disease temporally associated with the use of a drug, without any judgment about causality. An adverse event can arise from any use of the drug (e.g., off-label use, use in combination with another drug) and from any route of administration, formulation, or dose, including an overdose.

Suspected Adverse Reaction: Suspected adverse reaction means any adverse event for which there is a reasonable possibility that the drug caused the adverse event. For the purposes of IND safety reporting, 'reasonable possibility' means there is evidence to suggest a causal relationship between the drug and the adverse event. A suspected adverse reaction implies a lesser degree of certainty about causality than adverse reaction, which means any adverse event caused by a drug.

Reasonable Possibility: There is evidence to suggest a causal relationship between the drug and the adverse event.

Serious: An adverse event or suspected adverse reaction is considered "serious" if, in the view of either the investigator or sponsor, it results in any of the following outcomes: Death, a life-threatening adverse event, inpatient hospitalization or prolongation of existing hospitalization, a persistent or significant incapacity or substantial disruption of the ability to conduct normal life functions, or a congenital anomaly/birth defect. Important medical events that may not result in death, be life-threatening, or require hospitalization may be considered serious when, based upon appropriate medical judgment, they may jeopardize the patient or subject and may require medical or surgical intervention to prevent one of the outcomes listed in this definition. Examples of such medical events include allergic bronchospasm requiring intensive treatment in an emergency room or at home, blood dyscrasias or convulsions that do not result in inpatient hospitalization, or the development of drug dependency or drug abuse.

Unanticipated Problems Involving Risk to Subjects or Others (UPIRTSO)

Any unanticipated problem or adverse event that meets the following three criteria:

- **Serious:** Serious problems or events that results in significant harm, (which may be physical, psychological, financial, social, economic, or legal) or increased risk for the subject or others

(including individuals who are not research subjects). These include: (1) death; (2) life threatening adverse experience; (3) hospitalization - inpatient, new, or prolonged; (4) disability/incapacity - persistent or significant; (5) birth defect/anomaly; (6) breach of confidentiality and (7) other problems, events, or new information (i.e. publications, DSMB reports, interim findings, product labeling change) that in the opinion of the local investigator may adversely affect the rights, safety, or welfare of the subjects or others, or substantially compromise the research data, **AND**

- Unanticipated: (i.e. unexpected) problems or events are those that are not already described as potential risks in the protocol, consent document, not listed in the Investigator's Brochure, or not part of an underlying disease. A problem or event is "unanticipated" when it was unforeseeable at the time of its occurrence. A problem or event is "unanticipated" when it occurs at an increased frequency or at an increased severity than expected, **AND**
- Related: A problem or event is "related" if it is possibly related to the research procedures.

Adverse Event Reporting Period

The study period during which adverse events must be reported is normally defined as the period from the initiation of any study procedures to the end of the study treatment follow-up. For this study, the study treatment follow-up is considered the four month postoperative period following study drug administration.

Preexisting Condition

A preexisting condition is one that is present at the start of the study. A preexisting condition should be recorded as an adverse event if the frequency, intensity, or the character of the condition worsens during the study period.

General Physical Examination Findings

At screening, any clinically significant abnormality should be recorded as a preexisting condition. At the end of the study, any new clinically significant findings/abnormalities that meet the definition of an adverse event must also be recorded and documented as an adverse event.

Post-study Adverse Event

All unresolved adverse events should be followed by the investigator until the events are resolved, the subject is lost to follow-up, or the adverse event is otherwise explained. At the last scheduled visit, the local investigator should instruct each subject to report, to the local investigator, any subsequent event(s) that the subject, or the subject's personal physician, believes might reasonably be related to participation in this study. The local investigator should notify the study regulatory sponsor of any death or adverse event occurring at any time after a subject has discontinued or terminated study participation that may reasonably be related to this study. The sponsor should also be notified if the local investigator should become aware of the development of problems, cancer or of a congenital anomaly in a subsequently conceived offspring of a subject that has participated in this study.

Hospitalization, Prolonged Hospitalization or Surgery

Any adverse event that results in hospitalization or prolonged hospitalization should be documented and evaluated for relationship to the study drug/placebo. If there is a reasonable possibility that it is related to the study drug/placebo then will be reported as a serious adverse event unless specifically instructed otherwise in this protocol. Any condition responsible for surgery should be documented as an adverse event if the condition meets the criteria for an adverse event.

Neither the condition, hospitalization, prolonged hospitalization, nor surgery are reported as an adverse event in the following circumstances:

- Hospitalization or prolonged hospitalization for diagnostic or elective surgical procedures for a preexisting condition. Surgery should **not** be reported as an outcome of an adverse event if the purpose of the surgery was elective or diagnostic and the outcome was uneventful.
- Hospitalization or prolonged hospitalization required to allow efficacy measurement for the study.
- Hospitalization or prolonged hospitalization for therapy of the target disease of the study, unless it is a worsening or increase in frequency of hospital admissions as judged by the clinical investigator.

The expected adverse events from surgery include post-operative pain, nausea, vomiting, general anesthesia risks, hemorrhage, surgical site infection, mastectomy skin necrosis, seroma, surgical site paresthesia.

The table below will be used for collecting and grading serious adverse events associated with BTX-A injection.

Adverse Event	Grade				
	1	2	3	4	5
Cardiac dysrhythmia	Asymptomatic; intervention not indicated	Symptomatic; medical intervention indicated	Symptomatic and incompletely controlled medically, or controlled with device (e.g., pacemaker)	Life-threatening consequences; urgent intervention indicated	Death
Myocardial infection		Asymptomatic and cardiac enzymes minimally abnormal and no evidence of ischemic ECG changes	Severe symptoms; cardiac enzymes abnormal; hemodynamically stable; ECG changes consistent with infarction	Life-threatening consequences; hemodynamically unstable	Death
Dysphagia	Symptomatic, able to eat regular diet	Symptomatic and altered eating/swallowing	Severely altered eating/swallowing; tube feeding or TPN or hospitalization indicated	Life-threatening consequences; urgent intervention indicated	Death
Anaphylaxis			Symptomatic bronchospasm, with or without urticaria; parenteral intervention indicated; allergy-related edema/angioedema; hypotension	Life threatening consequences; urgent intervention indicated	Death
Seizure	Brief partial seizure; no loss of consequences	Brief generalized seizure	Multiple seizures despite medical intervention	Life-threatening; prolonged repetitive seizures	Death
Respiratory depression/		Decreased oxygen saturation with	Decreased oxygen saturation at rest	Life-threatening airway compromise;	Death

hypoxia		exercise; intermittent supplemental oxygen		urgent intervention indicated	
---------	--	--	--	-------------------------------	--

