8.4 Unblinding Procedures

In case of an adverse event, un-blinding of the study participant will be carried out immediately. The event will be analyzed in the same manner as any severe adverse drug reaction. This will be reported to the appropriate agencies with the analysis, conclusions and recommendations. The study will then

be re-instituted if given approval to continue. This study subject will be categorized as a treatment failure and imputed the most negative score on all outcomes.

All serious adverse events (SAE) will be reported, and un-blinding will be part of managing an SAE. The PI and the research team will continually review blinded data after each subject has study interaction, including a review of all adverse events, to determine seriousness and relation to study drug. Minor adverse events and unusual complications encountered during the period of tissue expansion will be carefully recorded. In the event of a serious adverse reaction to the treatment, the study participant will be treated accordingly depending on the reaction.

Any AE that occurs during the course of the study will be disclosed to the Mayo Clinic IRB. All SAE will be reported to the FDA as well as to Allergan within 15 calendar days after its first knowledge. The Principal Investigator will provide written notice to Allergan within 15 calendar days of any occurrence(s) of either (i) pregnancy or (ii) lactation during the time period of effect of BOTOX®, which can last three to four months.

In cases where un-blinding was not associated with an SAE, such actions will be reported in a timely manner. Notification of sponsor will be performed within 24 hours by phone or fax, followed by a written narrative of the event within 48 hours. The statistician conducting the interim analysis will contact Research Pharmacy personnel to proceed with un-blinding not associated with an SAE.

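### Section 8.1 makes a hospitalised adverse event serious whatever its cause, then reports it as an SAE only if judged related; Section 8.4 does not say whether that judgement comes before unblinding

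*Combined protocol and SAP*

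**What the plan says.** Section 8.1 defines an adverse event as something "temporally associated with the use of a drug, without any judgment about causality". The definition of serious covers both adverse events and suspected reactions ("An adverse event or suspected adverse reaction is considered" is how it opens), and one qualifying outcome is "inpatient hospitalization or prolongation of existing hospitalization". No causal link is required.

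The later subsection of 8.1 on hospitalisation and surgery says that an event leading to admission or a longer stay "should be documented and evaluated for relationship to the study drug/placebo". It continues: "If there is a reasonable possibility that it is related to the study drug/placebo then will be reported as a serious adverse event". It then lists exceptions: elective or diagnostic procedures for a preexisting condition, stays needed for efficacy measurement, and treatment of the target disease.

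Section 8.3.1 first requires any SAE to reach the IRB within 5 calendar days, and ends by limiting IRB reports to SAEs that are directly related.

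Section 8.4 states: "In case of an adverse event, un-blinding of the study participant will be carried out immediately". It makes unblinding part of SAE management. It also says that the investigator and team review blinded data to settle seriousness and relationship to study drug; Section 1.5 says the same.

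Section 8.6 bases medical monitoring partly on regular review of how many SAEs occur and of what kind.

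**The concern.** Seriousness and causality are different attributes. Seriousness is a fact about the outcome; causality is a judgement about one patient. In a randomised placebo-controlled trial, the comparison of all serious events by arm is what tests causality for events that are common after the operation anyway. If a case-level causality judgement decides which events enter the SAE count, the count no longer gives that comparison.

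The point has force here because the participants have all just had a mastectomy with expander placement. Section 8.1 notes that "The expected adverse events from surgery include post-operative pain, nausea, vomiting, general anesthesia risks, hemorrhage, surgical site infection", among other events. An admission for one of these may or may not be judged related to the injection, and two assessors following different parts of 8.1 would classify it differently. If the assessor knows the arm, the judgement can also differ systematically between arms.

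**Working it through.** The plan states no figure on this point, so the check is a comparison of its rules.

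**One case under each rule.** Take a participant readmitted for haemorrhage at the surgical site within the four-month reporting period, whom the assessor judges unrelated to the injection.

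- Section 8.1, definition of serious: inpatient admission is a qualifying outcome, so this is an SAE.
- Section 8.1, hospitalisation subsection: no reasonable possibility of relatedness, so it is not reported as an SAE. None of the listed exceptions applies, so they do not explain the difference.
- Section 8.2: recorded as an adverse event in the source document and the CRF.
- Section 8.3.1: reportable to the IRB if it is an SAE, by the general sentence; not reportable, by the closing sentence. Section 8.4 adds a third version, under which every adverse event is disclosed to the IRB.
- Section 8.6: counted if the SAE tally follows the definition of serious; not counted if it follows the events reported as SAEs.

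**Order of causality call and code break.** Section 8.4 contains an immediate code break on an adverse event and a blinded review of relatedness. Both can be honoured only if the review is completed first. No section says so, and none requires the causality call to be recorded before the code is broken.

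**What each defect would do to a count.** The following illustrates the mechanism and does not estimate it: every rate and share is assumed, and only the 64 per arm comes from the plan (Section 7.1). The true hospitalisation rate h is set equal in the two arms, so any difference in counts comes from classification alone. Expected SAEs per arm = 64 × h × share judged related.

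| h (assumed) | By outcome: 64 × h, per arm | Related only, judged blind (30% in both arms) | Related only, arm known (50% BTX-A, 10% placebo) |
|---|---|---|---|
| 5% | 3.2 v 3.2 | 1.0 v 1.0 | 1.6 v 0.3 |
| 10% | 6.4 v 6.4 | 1.9 v 1.9 | 3.2 v 0.6 |
| 15% | 9.6 v 9.6 | 2.9 v 2.9 | 4.8 v 1.0 |

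A blinded relatedness filter applied equally shrinks the count but keeps it balanced. A filter applied with the arm known can create an imbalance where none exists. With other shares it could as easily hide a real one.

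**The case against.** The case on the other side is substantial.

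- The hospitalisation subsection governs what is reported as an SAE. It can be read as a reporting filter that leaves classification alone.
- That subsection requires hospitalised events to be documented, and Section 8.2 requires every adverse event to be recorded. An all-cause count by arm could be rebuilt, provided the CRF captures hospitalisation.
- Section 8.5 compares surgical site infection between arms with a 15% absolute-difference stopping rule and no relatedness condition. Section 3.3 makes expander removal for any reason a secondary endpoint. Section 3.4 checks wound healing and tissue integrity in all patients at the first postoperative visit. Section 8.6.1 has an uninvolved statistician review unblinded adverse event data, not only SAEs.
- Section 8.3.1 already lists relationship and expectedness as separate items on the report.
- No by-arm SAE test is planned, and the primary safety endpoint is itself limited to attributable side effects.

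Most of this stands, and it limits the consequence. A reader might infer that a rise in readmissions on BTX-A would disappear from the trial. The documents do not support that: the events are recorded, and infection and expander loss are compared whatever their cause. A reader might also infer that most surgical readmissions would be judged unrelated because they are listed as expected. Expected does not mean unrelated, and no section says how such events would be judged.

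The conflict itself remains. The text nowhere says that the hospitalisation rule is only a reporting filter, and a tally of reported SAEs would follow it in either case. The separate all-cause views do not cover every readmission; one for haemorrhage without expander loss is an example.

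**Conclusion.** The contradiction in Section 8.1 is real, and no other section resolves it; Section 8.3.1 repeats it for the IRB. Followed as written, the hospitalisation rule leaves admissions judged unrelated out of the SAE number and type reviewed under Section 8.6. This is a rule to correct, not a missing detail.

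The size cannot be derived, because the documents give neither a hospitalisation rate nor a share judged related. The reach is confined to SAE monitoring and descriptive safety tables. The sample size is untouched.

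On unblinding, the supported statement is that causality may be judged with the arm known. That it will be goes too far, because Sections 1.5 and 8.4 also describe blinded review. A reader might further infer that SAE classification feeds the efficacy data, since Section 8.4 gives an unblinded participant the worst score on all outcomes. As written, that rule is triggered by an adverse event and not by its SAE status, so the link would need a practice that the documents do not describe.

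**What to change.** Reconcile four places.

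1. **Section 8.1, hospitalisation subsection:** remove the relatedness condition, so that an adverse event resulting in inpatient or prolonged hospitalisation is an SAE by outcome, in line with the definition of serious. The listed elective and planned exceptions can stay.
2. **Section 8.3.1, with the IRB sentence in 8.4:** state once which events go to the IRB and when. Use relatedness only to decide expedited reporting.
3. **Section 8.4:** set the order. Relatedness is recorded, with a date, in its own field before any non-emergency code break. The immediate-unblinding sentence has to be reconciled with the blinded-review sentence.
4. **Sections 7.2 and 8.6:** tabulate all SAEs by arm regardless of causality, with relatedness shown alongside. During the trial, by-arm tables go only to the uninvolved statistician and the DSMB.

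The cost is a few edited sentences across these sections, a somewhat longer SAE listing, and a hospitalisation item on the CRF if there is none. Sample size, visits and the efficacy analysis do not change.
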